recognize that resources available within each healthcare system will differ somewhat, as may the priorities, preferences and values expressed by key stakeholders at each project site. As a result, during the pre-rollout period each site's DALT will meet with the central research team to adapt the core elements as needed while concurrently maintaining high implementation fidelity. This process will be informed by the Dynamic Adaptation Process developed by Aarons et al., engaging multiple stakeholders to take into account the local context and resources.⁴⁸ During the pre-implementation period, each DALT will meet monthly via conference call with the central research team to discuss the core and supplemental intervention elements within the context of local system, organization, provider, and patient characteristics.⁴⁸ These discussions will be supported by review of local administrative data and pilot data of study outcomes, with tailoring of educational materials and tools as appropriate. During the implementation phase, the DALT and central research team will meet quarterly to discuss implementation fidelity and the need for potential adaptation.

Covariates. In addition to the above-described comparators, we will evaluate, at baseline, patient-level characteristics that may be associated with portal of hospital admission. These include: child age, gender, race/ethnicity, primary payer (Medicaid, commercial, other), primary reason for hospital admission (clinical condition), medical complexity, and level of care (observation or inpatient status). Medical complexity will be categorized as no concurrent chronic illness, chronic non-complex illness (i.e. diabetes, asthma),

or complex chronic disease (i.e. neuromuscular disease, technology dependence) by applying the validated Pediatric Medical Complexity Algorithm (PMCA).⁴⁹ All variables will be extracted from hospitals EHRs using standardized processes developed and piloted during the pre-rollout period.

4. Study Design & Randomization. To

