We will first determine crude differences in baseline clinical and sociodemographic characteristics, and in our primary and secondary outcomes, between children admitted directly and through EDs, using t-tests and chi-square tests as appropriate. However, because these unadjusted analyses do not adjust for observed predictors related to direct and ED admission, including temporal trends, for our main analyses we will use regression models. Because all patients receive some form of clinical care at the hospital irrespective of form of admission, there is no censoring associated with the measurement of time to clinical care. Therefore, standard regression models may be used. Patient characteristics incorporated in models will include diagnosis, medical complexity,⁴⁹ level of care (observation versus inpatient), as well as age, gender, race/ethnicity and payer. The statistical model for our direct patient-level comparison of direct admission (DA) versus ED admission patients (analysis i) is

$$Y_{ijht} = \beta_0 + \beta_1 D A_{ijht} + \beta_2 x_{ijht} + \beta_{3t} + \beta_{4h} + \theta_{jh} + \varepsilon_{ijht}$$

in which Y_{ijht} is the outcome variable for patient *i* seen by clinic *j* at hospital *h* at time *t*; DA_{ijht} is a binary variable indicating whether the patient was admitted via direct admission ($DA_{ijht} = 1$) or the ER ($DA_{ijht} = 0$), x_{ijht} is a vector of patient-level controls and θ_{jh} is a random effect for clinic within hospital. In addition, the model includes fixed-effects for time-period, β_{3t} , and hospital, β_{4h} , to capture the general unstructured trend across calendar time and hospitalspecific effects, respectively. The key coefficient of interest is β_1 , which captures the association of a patient being admitted directly versus by an ED with the outcome. A crucial feature of this analysis is that the predictor of primary interest, DA, varies within clinic and time-period mitigating almost all forms of clustering. Therefore, although the data are clustered by clinic and time, the primary source of information about the association of DA with the outcome is from contrasts within clinic and time-period. Hence, accounting for time-period and clinic effects is likely to strengthen the statistical significance of our results.

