When estimating the model in (i), for our primary analysis we plan to only use observations from the post-period. This avoids any contamination from outcomes of ED observations when DA was not available. However, to gain some insight into the closeness of the results from this analysis with those that we'd expect to see if it was possible to have patient-level randomization, in a supplemental analysis we will include the pre-intervention ED observations and test if there is a change in the mean ED outcome in the post-intervention period. A result consistent with minimal change over time will support a finding that, in the absence of the intervention, the outcomes for DA patients would have been the same as those observed for ED patients.

The statistical model for analysis (ii) has a similar form:

$$Y_{ijht} = \beta_0 + \beta_1 Post_{jht} + \beta_2 x_{ijht} + \beta_{3t} + \beta_{4h} + \theta_{jh} + \varepsilon_{ijht}$$

differing only in that the direct admission indicator is replaced with $Post_{jht}$, a time-varying practice within hospital indicator of whether the intervention has been rolled-out (1 = intervention transition has occurred by time period t and 0 = direct admission intervention has not occurred by time-period t). The key coefficient of interest is β_1 , which captures the structural shift in the outcome that occurs when a practice receives the direct admission intervention. Because $Post_{jht}$ does not vary within a clinic and time-period, the information in the observations made within a clinic and time-period depends on the size of the effects of clinic and time-period with the statistical significance of inferences about β_1 is likely to be reduced by the clustering of observations in clinics. An additional component of clustering arises because the four groups are aligned with nine practice groups that in turn are embedded in three hospitals. We acknowledge that there may be separate levels of clustering in the data due to hospital and below that due to practice groups.

However, the nine practice groups emanating from the 3 hospitals will be randomly distributed across the four groups of the stepped-wedge design in a manner that balances the four groups with respect to the characteristics of these groups. Because the practice groups and hospitals are cross-classified with the SWD groups, their effects on the statistical precision of the results will be much less than under a purely hierarchical arrangement.

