8. Sample Size and Power. Our projected sample size is shown in Table 5 and Figure 2. Based on the conservative assumptions above, we anticipate that 190 children and adolescents will be directly admitted and 1506 will be admitted through the ED. Of those admitted through the ED, 870 will be during post time-periods. Therefore, for analysis (i) there will be 190 direct admissions and 870 concurrent control ED admissions. Because the effect of all forms of clustering in analysis (i) of Aim 1 are minimal, we illustrate the statistical power for this analysis by using a two-group t-test. To inform our effect size determination, the PHM program at Lowell General Hospital (Lowell, MA), which has a well-established direct admission program, collected timeliness data from April-July 2018, applying the same eligibility criteria and definition proposed for this study. ED timeliness data was similarly derived from Lowell and PMRC-E. We found that mean time to clinical care for ED admissions was 85 min [SD 83 min], and mean time for direct admissions was 40 minutes [SD 28 min].

With the above means and standard deviations, a two-sided 0.05-level test that allows for unequal standard deviations performed in the context of analysis (i) of Aim 1 has power well in excess of 0.99. There is also substantial power for subgroup analyses. For example, the power of a subgroup analysis that involves 10% of the sample (applied evenly across clinics and time-intervals) has power of 0.98. It is only when the subgroup is as small as 5% that power falls below 0.80. These power calculations can be performed using self-calculation or a variety of software packages. In this instance, it was performed using Satterwaite's approximation (i.e., evaluating a pooled variance to approximate the sampling distribution of the actual test-statistic by a t-distribution) under nQuery.

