9. Outcomes. Our primary outcome, prioritized by multidisciplinary stakeholders including parents and healthcare teams in our preliminary work,³⁹ will be timeliness of clinical care provision. Timeliness of clinical care will be defined as the time from arrival at the hospital until initiation of clinical care by the accepting healthcare provider (including diagnostic testing and/or medical management). This outcome will be derived from EHR time stamps; all project sites use EHRs to document times of patient registration, orders, administration of medications and therapies, and diagnostic tests. EHR time stamps have been previously validated using time motion data;⁶⁸ during the pre-implementation period we will similarly validate the accuracy of time stamps by conducting time motion studies at each hospital.⁶⁹ The feasibility of collecting timeliness outcome data is supported by preliminary data from Lowell General Hospital and PRMC-E, as described above (see Power Calculation, effect size estimation).

Secondary outcomes will include: (i) parent-reported family experience of care (detailed below); (ii) unanticipated transfer to the ICU within 6 hours of hospital admission, a marker of clinical deterioration;³⁸ and (iii) rapid response calls within 6 hours of hospital admission, a second marker of clinical deterioration defined as calls to the hospital's medical-

Table 6. Consumer Quality Index Inpatient
Hospital Care admission module measures
Your rights as patient (complaint procedure,
etc.)
What will happen during this hospitalization
The person in the hospital whom you can
contact if you have questions
What medications you are taking
Any dietary and nutritional requirements
Any hypersensitivity to
substances/medication
Your provisional discharge date
Your personal needs during the
hospitalization
Did the healthcare providers/ staff, upon
arrival to the ward, have enough time for
you?

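### Observation-versus-inpatient status is adjusted for as a baseline covariate in the randomised model (ii), although it is set after the practice's randomised crossover and its timing is not defined

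*Combined protocol and SAP*

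**What the plan says.** Section D.3 (Covariates) says that "we will evaluate, at baseline, patient-level characteristics that may be associated with portal of hospital admission". The list that follows includes "level of care (observation or inpatient status") beside age, gender, race/ethnicity, payer, clinical condition and medical complexity. Section D.5, Aim 1, puts the same items into the regression models, including "level of care (observation versus inpatient), as well as age, gender, race/ethnicity and payer".

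Model (i) compares direct with ED admissions at patient level. Model (ii) estimates the effect of the practice having crossed over, and is described as "differing only in that the direct admission indicator is replaced with" the Post indicator. The covariate vector, level of care included, therefore stays in model (ii). The Aim 2 subgroup and interaction models are built on model (i), so they inherit it too.

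Nowhere does the plan say when status is recorded, or whether the first or the final status of the stay is extracted. No adjusted analysis omits it: the stated sensitivity and supplemental analyses concern missing data, the two added practices and the pre-intervention ED patients.

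**The concern.** Age, payer or chronic complexity exist before anyone decides how a child enters hospital. Observation or inpatient status is a property of the stay. Practices are randomised to a crossover time (Section D.4), so the status of any child admitted after crossover is set downstream of that assignment, at whatever hour it is recorded. The intervention also changes steps that could influence it: a structured judgement of suitability by the accepting physician, and rapid assessment by the inpatient team on arrival (Section D.3, Intervention Core Elements).

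Model (ii) is the only contrast in the plan that randomisation protects. Conditioning on a post-assignment variable that the intervention may change gives up part of that protection.

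The outcome definitions add to this. The primary outcome is the "time from arrival at the hospital until initiation of clinical care by the accepting healthcare provider", so status may be set while that clock is running or after it has stopped. Two secondary outcomes are unanticipated ICU transfer and rapid response calls within 6 hours of admission (Section D.9). If final status is the one extracted, early deterioration could itself change it, and those models would then adjust for a consequence of the outcome and could obscure a safety difference.

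**Working it through.** **Inputs from the plan (Section D.8).** For the ED route, "mean time to clinical care for ED admissions was 85 min [SD 83 min"]; for the direct route, "mean time for direct admissions was 40 minutes [SD 28 min"]. Model (i) has "190 direct admissions and 870 concurrent control ED admissions". Model (ii) has effective sample sizes of 444 (post) and 267 (pre), a post mean of 76.93 and a post SD of 84.99. The direct-admission share after crossover is 19/106 = 0.179. The plan prints that ratio as 0.094, but its post mean of 76.93 is obtained with 0.179, so 0.179 is used here.

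**Step 1: reproduce the plan's figures.**
- Route difference: 85 − 40 = 45 min.
- Post effect: 0.179 × 45 = 8.07 min, and 85 − 8.07 = 76.93, as printed.
- Model (ii) power: SE = √(83²/267 + 84.99²/444) = 6.49; 8.07/6.49 = 1.24; two-sided 0.05 power = 0.24 (0.237 by the Satterthwaite t), against a stated 0.23.
- Model (i): 45/√(28²/190 + 83²/870) = 12.97 standard errors, so power is about 1, in line with the stated value above 0.99.

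None of these calculations uses a covariate.

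**Step 2: what adjustment does if status lies on the pathway.** Let Δp be the change in the observation share caused by direct admission, and γ the observation-minus-inpatient difference in time to care.
- Model (i): the adjusted coefficient differs from the total effect by γ × Δp.
- Model (ii): only directly admitted children carry the shift, so the difference is 0.179 × γ × Δp (assuming no spillover to ED children).

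**Step 3: assumed values.** The documents give neither γ nor Δp. These are illustrations only.

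| γ | Δp (absolute) | Shift in (i), of 45 min | Shift in (ii), of 8.07 min | Share of effect |
|---|---|---|---|---|
| any | 0 | 0 | 0 | 0% |
| 20 min | 0.10 | 2 min | 0.36 min | 4.4% |
| 20 min | 0.20 | 4 min | 0.72 min | 8.9% |
| 40 min | 0.30 | 12 min | 2.15 min | 26.7% |

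The sign of Δp sets the direction. In the last row the model (i) effect moves from −45 to −33 or −57 min, and the model (ii) effect from −8.07 to −5.92 or −10.22 min. An effect of that size in model (ii) would have power 0.15 or 0.35.

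**Step 4: unmeasured severity.** If γ = 0, the shift is zero unless an unmeasured factor drives both status and time to care. A simulation of 400,000 children gave severity a 0.15 effect on status and a 20 min effect on time to care per SD, with severity unrelated to route. The unadjusted estimate stayed near −45 min. Adding status moved it to −47.2 min (Δp = 0.20) and −48.5 min (Δp = 0.30).

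**Step 5: status as a severity proxy in model (i).** A second simulation let severity influence route, status (0.15 per SD) and time to care (20 min per SD), with no effect of route on status and a true route effect of −45 min. The estimate was −31.8 min without status and −32.9 min with it. Here adjustment helps slightly.

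**The case against.** The strongest objection concerns model (i). That comparison is not randomised. Section D.5 adjusts it for observed predictors of the admission route, and Section D.7 says that ED children may be sicker or less stable. The conceptual framework (Figure 1) names disease severity, but the covariate list has no direct acuity measure, so level of care may be its closest stand-in. Dropping it could leave more confounding, as Step 5 shows. This stands: removing it from model (i) and the Aim 2 models is a trade-off between its roles as mediator and as confounder. The argument does not carry over to model (ii), where randomised crossover, with period effects in the model, is what protects the comparison.

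A second objection is that timing is unknown. For direct admissions status might be fixed at acceptance or on arrival. A reader might infer that status is decided after early care, or after the outcome has occurred, and that part of the effect is therefore removed. The documents support neither. Bias needs the intervention to change status, and status to be tied to the outcome directly or through unmeasured severity. This stands as a limit on certainty. It does not make the variable baseline with respect to the randomised crossover.

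A third concerns size. A reader might set the 2 to 4 min route-level figure against the 8.07 min Post effect and conclude that a quarter to a half of it is lost. That mixes scales, because the route shift reaches only 17.9% of post-period children. A 10 to 20 point shift across all post-period children would need a route shift of 0.10/0.179 to 0.20/0.179, that is 56 to 112 points, unless ED children's status also changed. Section D.8 raises spillover only as a possibility, and only for the outcome.

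Finally, Section D.5 does plan crude comparisons by route without this covariate. They carry no other adjustment and do not address the Post effect.

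**Conclusion.** The point holds in a limited form. Level of care is labelled baseline and adjusted for in both models, although it describes the stay and is set after the practice's randomised crossover; when it is recorded, and which status is used, are undefined. In model (ii) this exposes the randomised contrast to an avoidable bias of unknown sign. For ICU transfer and rapid response there is the further risk, if final status is used, of adjusting for a consequence of the outcome.

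The size cannot be taken from the documents. With a 20 min difference by status and a 10 to 20 point shift by route, both assumed, it is 4 to 9% of the effect in each model. The wider assumed range reaches 27% either way, and it is zero if the intervention does not change status. It does not threaten the power of model (i). A reader might go further and say that the covariate should leave every model; the documents do not support that for model (i) or Aim 2, where status may partly represent severity.

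**What to change.** 1. Remove level of care from the covariate vector of the main model (ii) for all outcomes, and keep it only in a sensitivity analysis labelled as adjusting for a post-assignment variable.
2. Report model (i) and the Aim 2 models both with and without it, and say that the two versions bracket a choice between mediator and confounder roles. If severity measured at referral or arrival is available in the EHR, use that as the acuity covariate.
3. In Section D.3, stop describing level of care as baseline. State when it is recorded and whether first or final status is extracted.

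Cost: a few sentences of SAP wording, a few extra model runs and possibly a small loss of precision from dropping one covariate in model (ii). No stated sample size or power figure changes, because the power calculations use no covariates.

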1. Summary. We will conduct a stepped-wedge cluster randomized controlled trial to evaluate outcomes associated with a direct admission intervention at three health systems: Children's Hospital of Pittsburgh (CHP) in Pittsburgh, Pennsylvania, Nationwide Children's Hospital (NCH) in Columbus, Ohio, and Providence Regional Medical Center (PRMC-E) in Everett, Washington. We have partnered with these health systems given their structural diversity, current low direct admission rates, and strong institutional support to implement and evaluate direct admission processes. A total of 70 practices affiliated with these hospitals will be randomized to cross over from ED admission (usual care at these hospitals) to the direct admission intervention at 4 time points, stratified by practice group. Given 3 practice closures and mergers during the first year of the project, an additional 2 practices will be randomized to participate in the second half of the project. Our primary outcome will be timeliness of clinical care provision. Secondary outcomes include family-reported experience of care and two measures of clinical deterioration: unplanned transfer to the ICU and rapid response calls within 6 hours of hospital admission. We will compare outcomes in children and adolescents with five common diagnoses from practices randomized to the direct admission intervention to those admitted from practices not yet eligible for the intervention, adjusting for appropriate covariates.

2. Conceptual Framework. Direct admission to hospital has several prerequisites, including access to timely ambulatory care for children with acute illnesses, and communication between outpatient and inpatient healthcare providers to initiate direct admission referrals. Our research approach reflects these prerequisites and is modified from Donabedian's structure, process, outcome framework to also incorporate patient characteristics and family preferences (Figure 1).⁴⁵ This framework illustrates how systems factors and processes of care may influence where children access ambulatory care for acute illnesses (ED or primary care clinic) and whether admission occurs directly or through the ED. These factors, in turn, influence health outcomes. The System Factors summarized in this model, including clinic and ED factors, were described by parents of hospitalized children as influential to their decisions about when and where they

pcori

seek

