TIME (0-50 month project period; each block represents 6 months unless otherwise specified; the 27mo and 36mo blocks are projections estimated from enrollment to date)

-----Rollout period-----Maintenance

pcori

PRINCIPAL INVESTIGATOR: [name]

very minimal program updake at CHP, we will not evaluate program maintenance at CHP. Figure 2b summarizes our anticipated additional recruitment of patients admitted directly and via emergency department admission at NCH and

PRMC-E, with numbers estimated from actual enrollment to date.

We will randomize 70 primary and urgent care practices: 18 at NCH, 34 at CHP, and 18 at PRMC-E (*Please see LOS from PCP practices affiliated with each hospital*). Practices in each group will be randomized using a stratified approach, with 17-18 practices (4-9 practices per hospital) randomized to crossover to the direct admission intervention at each step/crossover point, stratified by hospital and practice group. Given the closure or merger of 3 practices during the first project year, an additional 2 practices will be randomized to either Group 3 or Group 4, beginning during the 18 month block (Block 3).

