Structure of Study Sites: CHP has a Pediatric ED with an annual volume of over 80,000 visits and a PHM Service that provides care to > 9000 children each year. At CHP, the ambulatory care partners will be Pediatric Alliance (11 practices), Kids Plus Pediatrics (3 practices), Children's Community Pediatrics (18 practices including 14 primary care and 4 urgent care), and General Academic Pediatrics (2 practices). These practices are affiliated with CHP as part of a regional Pediatric Clinical Integrated Network. Excluding General Academic Pediatrics, these practice groups are independently owned and operated. NCH has a Pediatric ED annual volume of >90,000 visits, and a PHM Service that provides care to 6000 children each year. At NCH, the ambulatory care partner will be their NCH-owned Primary Care Network of 12 clinics, and 6 NCH-owned urgent care centers. [name], Site Principal Investigator at NCH is Division Chief in Hospital Medicine; he is fully supportive of randomizing their 12 primary care practices for this project. Finally, **PRMC-E** is a general hospital in Everett, Washington, where PHM services are provided by the Division of PHM at Seattle Children's Hospital. At this hospital, children seeking care in their ED are cared for in a general (non-children's) ED by general (non-pediatric) emergency medicine physicians. **PRMC-E** admits approximately 650 children annually. The ambulatory care partners at this site include the three primary care groups that together account for two-thirds of PRMC-E's referrals: The Everett Clinic (TEC), comprised of 10 pediatric primary care practices; the Providence Medical Group (PMG), comprised of 6 pediatric primary care practices; and Community Health Clinics of Snohomish County (CHC), comprised of 2 pediatric primary care practices.

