English, Spanish, Somali, Nepali or Arabic. (This response rate aligns with past work requesting parental participation in a survey during their hospital stay^{64,65}). To collect this parent-reported outcome, we will approach parents/guardians during their child's hospital stay, either by phone or in-person, keeping with each site's COVID-19 regulations. A research assistant will explain the study, and administer the survey via tablet or via personal cellphone to those parents/guardians who provide informed consent. Our sample size estimate for the relative number of direct admissions is dependent upon three assumptions/components of the direct admission process – first, that approximately 13% of children who are admitted to hospital will be seen by their PCPs prior to hospital admission (an

estimate derived from administrative data at NCH); second that these PCPs will contact the hospital for direct admission (a component of our direct admission intervention education); and third, that the PHM service will deem the child appropriate for direct admission and have a bed available. For this third criteria, we conservatively estimate that 80% of children referred for direct admission from PCPs will be accepted. Based on these assumptions, we estimate that 10% of children cared for by these PCPs will be directly admitted following rollout (Figure 2). Please note that our estimate that 13% of children who are admitted to hospital will be seen by their PCP is conservative; our PCP stakeholder partners have estimated that between 15 and 50% of their admitted patients are seen in their clinics prior to admission. For children considered for direct admission from urgent care centers, we anticipate that eligible urgent care providers will call to request direct admission in 80% of cases, and that 80% of these patients will be accepted. Our projected sample size of children admitted through the ED takes into account our assumption that these children may be more acutely unwell and/or clinically unstable. Correspondingly, we estimate that 70% of children who are admitted through the ED at children's hospitals with our target conditions will be eligible for inclusion, and that 95% of those who are admitted through the ED at our community hospital will be eligible for inclusion (given lower levels of acuity of children admitted to community hospitals).

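### Analysis (ii) omits the practice-group strata used in randomisation: list those strata and use them in place of the hospital effect

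*Combined protocol and SAP*

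**What the plan says.** Section D.1 has practices crossing over "to the direct admission intervention at 4 time points, stratified by practice group". Section D.4 gives the allocation as "stratified by hospital and practice group".

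Section D.5 writes out two models for Aim 1. Analysis (i) has the direct-admission (DA) indicator, patient-level covariates, a random effect for clinic within hospital, and fixed effects for period and hospital "to capture the general unstructured trend across calendar time and hospitalspecific effects, respectively". Analysis (ii) has the same terms with Post, the practice-level rollout indicator, in place of DA.

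The text under analysis (ii) then says: "We acknowledge that there may be separate levels of clustering in the data due to hospital and below that due to practice groups". Its answer is that "the nine practice groups emanating from the 3 hospitals will be randomly distributed across the four groups of the stepped-wedge design" in a balanced way, so that the effect on precision should be small. No term is added to either equation.

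**The concern.** When allocation is stratified, the strata normally enter the analysis. Stratifying reduces the true sampling variation of the treatment effect. A model without the strata does not credit that reduction, so its standard error is somewhat too large. The plan stratifies on practice group, accepts that practice groups may differ, and then adjusts only for hospital, one level above.

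At stake is precision in analysis (ii), the comparison that rests on the randomisation and the one with low stated power. Analysis (i) is a different matter. DA is not randomised, so a practice-group term there would be adjustment for possible confounding, not recovery of a stratified design.

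**Working it through.** **1. The strata.** Section D.6 gives these practice counts:

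- CHP: 11 + 3 + 18 + 2 = 34, in four groups. The group of 18 is "18 practices including 14 primary care and 4 urgent care".
- NCH: 12 primary care + 6 urgent care = 18.
- PRMC-E: 10 + 6 + 2 = 18, in three groups.

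The total is 34 + 18 + 18 = 70. Section D.5 counts nine groups. Section D.6 gives 4 + 2 + 3 = 9 only if the NCH primary care network and the NCH urgent care centres were separate strata; otherwise it gives 4 + 1 + 3 = 8. Groups of 3, 2 and 2 practices cannot be present in all four crossover groups, so the balance that D.5 relies on is incomplete.

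**2. The plan's own power for (ii).** The D.8 inputs, taken as stated, are means 85 and 76.93, SDs 83 and 84.99, and effective sample sizes 267 (pre) and 444 (post).

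- Effect = 85 − 76.93 = 8.07
- SE = √(83²/267 + 84.99²/444) = 6.49
- Power = Φ(8.07/6.49 − 1.96) + Φ(−8.07/6.49 − 1.96) = 0.238, against the stated 0.23

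The figure reproduces, and nothing in it depends on a practice-group term.

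**3. Adding the strata, with the plan's ICC divided between levels.** This is a generalised least squares calculation for 70 practices × 4 periods, with 1,696/280 = 6.06 patients per cell and total SD 83. It averages over stratified allocations using the nine groups above. The total ICC is 0.05. The share lying between practice groups is not in the documents, so it is varied. A share s corresponds to a practice-group SD of 83 × √(0.05 × s).

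| Share (SD, min) | Planned model SE | True SE of planned estimate | SE with strata | Ratio of SE, strata to planned | Type I error, planned | Power, planned → strata |
|---|---|---|---|---|---|---|
| 0% (0) | 5.86 | 5.86 | 5.89 | 1.005 | 0.050 | 0.28 → 0.28 |
| 25% (9.3) | 5.86 | 5.75 | 5.75 | 0.980 | 0.046 | 0.28 → 0.29 |
| 50% (13.1) | 5.87 | 5.65 | 5.58 | 0.952 | 0.042 | 0.27 → 0.30 |
| 75% (16.1) | 5.86 | 5.53 | 5.33 | 0.911 | 0.038 | 0.27 → 0.33 |

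The starting power differs from 0.238 because the SE comes from the fitted model, not from the plan's effective sample size. At ICC 0.10 the strongest case gives a ratio of 0.898.

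**4. Adding the strata at Figure 2b sizes.** This is a simulation with period totals 459, 301, 714, 775 and 540, the last at NCH and PRMC-E only. The assumed practice-group SD is 5, 15 or 30 minutes. The ratio of the SE without the strata to the SE with them was:

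- ICC 0.05: 1.00 / 1.01 / 1.04. The largest is 1 − 1/1.04 = 4% smaller with the strata.
- ICC 0.01: 1.00 / 1.05 / 1.10. The largest is 1 − 1/1.10 = 9% smaller.

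Applied to the SE of 6.49, a ratio of 1.04 gives SE 6.24 and power 0.25; 1.10 gives SE 5.90 and power 0.28. The planned model rejected a true null in 3% to 6% of runs. At the superseded Figure 2a sizes the most extreme setting (30 minutes, ICC 0.01) gave a ratio of 1.14 and power 0.30.

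**The case against.** The plan does not ignore practice groups. It names them and argues that balanced allocation limits their effect on precision, and the clinic intercept absorbs their variance in any case. Most of this stands: the test is valid, the gain is small, and no conclusion of (ii) turns on it. What does not stand is the balance argument as a reason to leave the term out. Balance lowers the true sampling variation, but the fitted SE does not show it (5.86 against a true 5.53 at a 75% share). Three of the strata are also too small to balance across four crossover groups.

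A reader might infer something stronger: that the DA coefficient in (i) is biased because urgent care uses direct admission far more than primary care. Section D.7 expects that "eligible urgent care providers will call to request direct admission in 80% of cases, and that 80% of these patients will be accepted", which is 0.80 × 0.80 = 64%, while for primary care "we estimate that 10% of children cared for by these PCPs will be directly admitted following rollout", from 13% × 80%. These figures have different denominators. The 64% is of urgent-care children considered for direct admission; the 10% is of all admitted children of these practices, of whom only about 13% are seen first. Among primary-care children who are seen and referred, the plan's acceptance figure is 80%. The documents therefore do not establish higher uptake in urgent care. They also give no difference in time to care between children from urgent and primary care at the same hospital. Bias needs both. Section D.5 adds that information on DA comes mainly from contrasts within clinic and period. Confounding between practice groups remains possible in (i), because DA is not randomised and a random intercept keeps part of the between-clinic contrast, but no size or direction can be given.

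**Conclusion.** The mismatch between randomisation and model is real, and its consequence is modest. In (ii), including the strata changes the SE of Post by between +0.5% (no practice-group differences) and about −4% at the plan's ICC in the Figure 2b simulation, and by up to about −9% to −10% under other assumed variances. The power gain is at most about four points at Figure 2b sizes and about six in the other calculations. Analysis (ii) stays underpowered either way. These ranges rest on assumed practice-group variances, which the documents do not give, and on nine strata, which the documents do not fully confirm.

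Type I error is not inflated; the planned test is at most slightly conservative. No stated power figure becomes wrong. For (i) no magnitude of bias is claimed. The point is worth considering because the change is nearly free and requires the strata to be written down before analysis.

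**What to change.** 1. List in the SAP the practice-group strata actually used, and say whether the NCH primary care network and urgent care centres were separate. Assign each of the two practices added at CHP to the practice group to which it belongs.
2. In analysis (ii), replace the hospital fixed effect with fixed effects for those strata and keep the clinic random effect. Practice groups are nested in hospitals, so the strata absorb the hospital effect.
3. For consistency, use the same term in analysis (i) and in the pooled Aim 2 interaction model. Keep the hospital term in separate fits for small subgroups, where the strata would raise the model SE by about 1% to 3% for an 11% subgroup (urinary tract infection) and 5% to 6% for a 3% subgroup (influenza).
4. Optionally, add an urgent-care versus primary-care indicator to (i) as a sensitivity analysis. The strata alone cannot separate the two in the CHP group that contains both.

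The cost is SAP wording and six extra parameters if there are nine strata (nine in place of three hospitals). Practice membership is already held for randomisation. If practice groups do not differ, the SE of Post rises by about 0.5%. The SE of DA in (i) rises by 0% to 1.3% at Figure 2b sizes, and the pooled Aim 2 interaction SE is unchanged.
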